## Parameters to be Evaluated in the NIPRIMUNE Phase 1 Clinical Trial

- 1. Demographic and Baseline Characteristics: Collecting data on participants' age, sex, weight, and medical history.
- 2. Vital Signs: Vital signs, such as blood pressure, heart rate, and temperature.
- 3. Laboratory Parameters: Laboratory tests, such as blood chemistry, hematology, and urinalysis will be carried out on volunteers.
- 4. Electrocardiogram (ECG): Cardiac function and rhythm.
- 5. Safety and Tolerability: Critical observation of adverse events (AEs) and serious adverse events (SAEs).
- 6. Pharmacokinetics (PK): Absorption, distribution, metabolism, and excretion (ADME) of NIPRIMUNE will determined using developed markers.
- 7. Maximum Tolerated Dose (MTD): The highest dose that can be safely administered will be determined.
- 8. Pharmacodynamics (PD): The general effect of NIPRIMUNE on the body.
- 9. Immunogenicity: Evaluating the immune response to NIPRIMUNE.

## Ethical Approval, Consent, Confidentiality, and Withdrawal

Ethical approval will be obtained from the National Health Research Ethics Committee of Nigeria, Federal Ministry of Health (NHREC). Informed written consent and assent will be obtained from participants.

*Consent:* The evaluation procedure will be explained to each subject and a written consent will be signed or thumb-printed before enrollment for the evaluation. Subjects may withdraw voluntarily at any point of evaluation.

Adverse Events: Adverse events are any undesirable experiences or events, which occur during the study or during a reasonable time thereafter, whether or not considered related to administration of the drug. Serious Adverse Events

Serious adverse events should be reported within 24 to 48 hours. This will ensure that other investigators are promptly cautioned

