#### Introduction

This is a Phase I clinical study of NIPRIMUNE, the Investigational Medicinal Product (IMP). The current study is designed to evaluate the safety and tolerability and pharmacokinetics of single and multiple oral doses of the IMP NIPRIMUNE, in healthy volunteers.

This phase 1 clinical trial is being undertaken to determine the safety of NIPRIMUNE in healthy human participants. Physical well-being, including laboratory investigations, will be closely monitored and evaluated. The clinical trial will be carried out in NIPRD Research Clinic and other accredited laboratory. The use of appropriate health diary by the patients will be introduced in the study.

NIPRIMUNE is a phyto-medicine that has demonstrated positive outcomes during in vitro and in vivo studies with anti-inflammatory ,antiviral and strong immunomodulatory characteristics.

This clinical study is planned as a double blind, randomised, placebo-controlled, combined clinical study of two parts: Single Ascending Dose (SAD) and Multiple Ascending Dose (MAD) studies, respectively. Pharmacokinetic (PK) profile of the NIPRIMUNE, will also be assessed in both parts of the study. The safety, tolerability and pharmacokinetic data and results obtained from this study will determine the potentially efficacious doses of the IMP NIPRIMUNE in the subsequent efficacy studies.

Between each cohort, an interim analysis of PK, safety and tolerability will be performed. The available data will be evaluated by an independent Drug Safety Monitoring Board (DSMB). Once a dose level is judged to be safe, the DSMB will allow the escalation to the next cohort.

Both the Investigator and study participants will remain blinded to the treatment administered (drug or placebo) till the final results of the study are obtained.

DSMB will provide recommendations about stopping, modifying or continuing the study. Decision to escalate to next dose level/ Cohort, will be based on interim analysis of pharmacokinetic data, 36-hr post-dose, and 30-days post dose safety follow-up.

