## **Study Design**

**Interventional Model Description:** Phase I, Randomized, Double-blind, Placebo-controlled, Single Ascending Dose and Multiple Ascending Dose Clinical Study to Assess the Safety, Tolerability and Pharmacokinetics of the Investigational Product in Healthy Adult Volunteers

Both the Investigator and study participants will remain blinded to the treatment administered (drug or placebo) till the final results of the study are obtained.

The placebo will identical to the investigational medicinal product in smell, taste, and appearance.

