#### **Arms and Interventions**

Participant Group/Arm	Intervention/Treatment
Experimental: NIPRIMUNE is a phytomedicine that has demonstrated positive outcomes during in vitro and in vivo studies for immune	NIPRIMUNE is a small molecule with demonstrated antiviral and immunomodulatory activity in-vitro & in

Participant Group/Arm	Intervention/Treatment
booster with antiviral charactreristics	vivo studies., it was anticipated that NIPRIMUNE can also be a promising immune booster
Formulated as Capsules intended for oral dosing to trial participants.	
Placebo Comparator: Placebo  placebo will be identical in smell, taste, and appearance to the Capsule of NIPRIMUNE	Placebo capsules identical in appearance, taste and smell to the capsules of NIPRIMUNE

This clinical study is planned as a double blind, randomised, placebo-controlled, combined clinical study of two parts: Single Ascending Dose (SAD) and Multiple Ascending Dose (MAD) studies, respectively. Pharmacokinetic (PK) profile of the NIPRIMUNE, will also be assessed in both parts of the study. The safety, tolerability and pharmacokinetic data and results obtained from this study will determine the potentially efficacious doses of the IMP NIPRIMUNE, in the subsequent efficacy studies.

Fifty six (56) healthy volunteers will be recruited age for sex. Randomised, The SAD Part will consist of 5 cohorts of 8 healthy adult volunteers, each volunteer will be randomly (blinded) allocated to NIPRIMUNE or placebo (each cohort will consist of 6 volunteers receiving NIPRIMUNE and 2 volunteers receiving placebo). Five (5) dose level of the investigational medicinal product are selected for oral administration. The MAD Part will consist of 2 cohorts of 8 healthy adult volunteers, each volunteer will be randomly (blinded) allocated to NIPRIMUNE or placebo (each cohort will consist of 6 volunteers receiving NIPRIMUNE and 2 volunteers receiving placebo). Two (2) dose levels of the investigational medicinal product are selected for oral administration. Additional Volunteers will be enrolled to replace(volunteers withdrawing consent from the study for reasons other than safety). Additional volunteers will also be enrolled if a Cohort needs to be repeated.

Safety evaluation during both the SAD & MAD pars of the clinical study will include adverse events, clinical laboratory/ pathological test results, electrocardiogram (ECG), and measurement of vital signs.

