Pharmacokinetics will be determined at pre-dose, and 30 min, 1h, 2h, 4h, 8h, 12h, and 24, post-dose, and 36 hrs post-dose on Day 2, for the SAD Part of the Study.

Pharmacokinetics will be determined at pre-dose, and 30 min, 1h, 2h, 4h, 8h, 12h, and 24h, of Day 1 and Day 7, at pre-dose on Days 2-6 and 36 hrs post final dose of Day 7 for the MAD Part

Safety analysis: frequency and severity of adverse events. The sample size is estimated to produce a good clinical effect at a 95% confidence and a power of 90. The participants will be randomized into two groups labeled A and B.

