## Primary outcome measures

Outcome Measure	Measure Description	Time Frame
Number of participants with adverse events [Time Frame-]	To assess safety & tolerability of NIPRIMUNE in Human	30 days post last dose for each cohort
Incidence of serious adverse events (SAEs) by relation to the IMP (related/not related)	To assess safety & tolerability of NIPRIMUNE in Human	30 days post last dose for each cohort
Percentage of volunteers who experience at least 1 Treatment Emergent Adverse Event (TEAE)	To assess safety & tolerability of NIPRIMUNE in Human	30 days post last dose for each cohort
Percentage of volunteers who discontinue due to an Adverse Event (AE).	To assess safety & tolerability of NIPRIMUNE n Human	30 days post last dose for each cohort
Percentage of volunteers who meet the markedly abnormal criteria for safety laboratory tests at least once post dose.	To assess safety NIPRIMUNE in Human	7 days post last dose for each cohort

Outcome Measure	Measure Description	Time Frame
Percentage of volunteers who meet the markedly abnormal criteria for vital sign measurements at least once post dose	To assess safety NIPRIMUNE in Human	7 days post last dose for each cohort
Percentage of volunteers who meet the markedly abnormal criteria for safety electrocardiogram (ECG) parameters at least once post dose.	To assess safety NIPRIMUNE in Human	7 days post last dose for each cohort

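### The SAE limit accepts a report at 48 hours, the blind is stated with no emergency exception, and no visible text brings an SAE to the DSMB while a MAD cohort is still being dosed

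*Protocol*

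**What the plan says.** Three parts of the protocol bear on what happens when a volunteer has a serious adverse event.

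- **Reporting.** Ethical Approval, Consent, Confidentiality, and Withdrawal: "Serious adverse events should be reported within 24 to 48 hours. This will ensure that other investigators are promptly cautioned". The passage gives neither a recipient nor the moment from which the hours are counted.
- **DSMB.** The Introduction to the Phase 1 trial says: "Between each cohort, an interim analysis of PK, safety and tolerability will be performed". An independent DSMB evaluates the data, and the decision to move up a dose "will be based on interim analysis of pharmacokinetic data, 36-hr post-dose, and 30-days post dose safety follow-up". A separate sentence, with no timing attached, says: "DSMB will provide recommendations about stopping, modifying or continuing the study".
- **Blind.** Study Design says that investigator and participants "will remain blinded to the treatment administered (drug or placebo) till the final results of the study are obtained". The Introduction contains the same sentence. Neither adds an exception.

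On dosing, Arms and Interventions says: "The MAD Part will consist of 2 cohorts of 8 healthy adult volunteers". Samples in that part are taken on Days 1 and 7, then "at pre-dose on Days 2-6 and 36 hrs post final dose of Day 7 for the MAD Part", so treatment runs from Day 1 to Day 7.

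**The concern.** All participants are healthy volunteers with no expected personal benefit, and safety is the primary outcome. Rules for handling an SAE are what protect them, and they belong in the protocol, so a statistical analysis plan that is not shown would not be expected to supply them.

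A range used as a deadline is only as strict as its upper end. The stated aim, warning other investigators promptly, also needs someone to receive the report and pass it on. A DSMB with power to stop or modify can use it during a cohort only if it hears of the event during that cohort. This matters most in the MAD part, where doses are still to come. The blind is a separate matter: a physician treating an emergency has no written permission to learn what that one person received, even where the answer would change care.

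**Working it through.** No figure in the protocol needs reproducing here. The check sets the texts side by side and counts the volunteers concerned.

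**1. The deadline.** The section gives 24 to 48 hours. The latest compliant report is at the upper end, 48 hours, which is 48 − 24 = 24 hours later than a plain 24-hour rule would allow. Because no starting point is given, this describes the permitted window and not the time elapsed since the event.

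**2. The recipient.** None is named in the text at hand. The DSMB and the regulator (NAFDAC) appear together in Budget for Clinical Trial, but only as a cost line that creates no reporting duty. Data Collection Forms lists a form for adverse experiences, whose content is not shown. Contact pages and one other part of the document were removed before review. The absence is therefore established for the visible text only.

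**3. The DSMB's information.** Two statements in the Introduction have to be read together:

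| Statement | Timing given |
|---|---|
| Interim analysis, evaluated by the DSMB | Between cohorts |
| Recommendations on stopping, modifying or continuing | None |

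The second statement does not limit the board to cohort ends. But nothing visible sends an SAE to the board within a cohort, and nothing visible asks the site to pause dosing after one.

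**4. Who is exposed to further dosing.** Inputs are from Arms and Interventions.

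- Single-dose (SAD) part: 5 × 8 = 40 volunteers, one dose each.
- MAD part: 2 × 8 = 16 volunteers, dosed over Days 1 to 7.
- Total: 40 + 16 = 56.

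Continued dosing of a running cohort is thus a MAD matter: 16 of 56 volunteers. Within such a cohort, an SAE on Day d leaves 7 − d scheduled dosing days: 6 after Day 1, 1 after Day 6, none after Day 7. These are counts of days on the schedule. They do not estimate doses that would be given because of the 48-hour limit, since the site may withhold treatment itself.

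**5. The blind.** The sentence stands in the Introduction and in Study Design, is unqualified both times, and has the final results as its only end point. No visible section describes a code break. Followed to the letter, the investigator stays blinded in an emergency as well.

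**The case against.** The best case against the point is that only the reporting window and the blinding sentence are stated rules, and the rest argues from silence. Much of this is right and limits what can be said.

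- **A reader might infer that the DSMB reviews safety only between cohorts.** The Introduction does not say so. It times one kind of review there and separately gives the board an untimed power to recommend stopping or modifying. The gate it describes is also protective: no higher dose starts before the board has judged the current one. What stands is narrower: no visible text carries an SAE to the board during a cohort.
- **A reader might compute a delay of days or weeks from SAE to review.** Any such figure depends on when the board meets and what it has already been told, and the protocol fixes neither. It would also mix time to a report with time to a review. No delay figure is supported.
- **A reader might conclude that no recipient exists.** Text was removed and the adverse-experience form is not shown, so the recipient may be named there.
- **A reader might conclude that a code break is forbidden.** Neither sentence says that. Mechanics are often kept in a randomisation or pharmacy procedure, which may exist here. Still, an unqualified sentence in the protocol should not contradict such a procedure.
- **A reader might picture dosing continuing regardless.** The primary outcomes count volunteers who discontinue for an adverse event, and a discontinuation form is listed, so individual stopping is foreseen. Neither is a rule for holding the rest of the cohort.

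**Conclusion.** The point holds in a limited form. Two stated rules are weaker than they need to be for healthy volunteers: the reporting limit, under which 48 hours is compliant despite the aim of prompt warning, and the blind, which is worded with no emergency exception. In addition, no visible text brings an SAE to the DSMB while a MAD cohort is being dosed, which concerns 16 of the 56 volunteers.

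This rests on the visible text and on MAD dosing from Day 1 to Day 7, as the sampling schedule implies. No endpoint, sample size or analysis is affected, and the trial's validity is not in question. It is a cheap improvement, best made before the first dose.

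**What to change.** Three changes of wording:

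1. **Ethical Approval, Consent, Confidentiality, and Withdrawal.** Replace the reporting sentence with: *Serious adverse events will be reported to the sponsor and the DSMB within 24 hours of site awareness.* This gives one limit, named recipients and a starting point.
2. **Introduction to the trial.** Add that an SAE that is possibly related or unexplained triggers prompt DSMB review, and that further dosing in that MAD cohort is held until then. Clearly unrelated SAEs are reported without a hold. The primary outcomes already require "Incidence of serious adverse events (SAEs) by relation to the IMP (related/not related", so a relatedness judgement has to be made anyway.
3. **Introduction and Study Design.** After the blinding sentence add: *except that one participant's code may be broken in a medical emergency where knowing the treatment affects care; each break is logged and the participant stays in the safety data.*

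The cost is this wording and a code-break procedure. There are three downsides. The DSMB would occasionally be contacted outside its planned reviews. A hold could interrupt dosing in a MAD cohort with 6 active volunteers, which would affect that cohort's Day 7 AUC0-tau and accumulation ratio. Any participant whose code is broken loses the blind.

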## **Response Outcome Measures**

## Current Primary Outcome Measures:

Determine the safety, tolerability, and dose-limiting toxicities of medication. Determine the safety, tolerability, and dose limiting toxicities of NIPRIMUNE Assessed by frequency and severity of adverse events(AEs), and changes in vital signs, 12-lead ECGs and laboratory assessments as compared to baseline [Time Frame: From the time the participant is administered the first dose through the final follow up clinic visit, for a total of 12weeks

## Primary outcome measures

Outcome Measure	Measure Description	Time Frame
Number of participants with adverse events [Time Frame-]	To assess safety & tolerability of NIPRIMUNE in Human	30 days post last dose for each cohort
Incidence of serious adverse events (SAEs) by relation to the IMP (related/not related)	To assess safety & tolerability of NIPRIMUNE in Human	30 days post last dose for each cohort
Percentage of volunteers who experience at least 1 Treatment Emergent Adverse Event (TEAE)	To assess safety & tolerability of NIPRIMUNE in Human	30 days post last dose for each cohort
Percentage of volunteers who discontinue due to an Adverse Event (AE).	To assess safety & tolerability of NIPRIMUNE n Human	30 days post last dose for each cohort
Percentage of volunteers who meet the markedly abnormal criteria for safety laboratory tests at least once post dose.	To assess safety NIPRIMUNE in Human	7 days post last dose for each cohort

Outcome Measure	Measure Description	Time Frame
Percentage of volunteers who meet the markedly abnormal criteria for vital sign measurements at least once post dose	To assess safety NIPRIMUNE in Human	7 days post last dose for each cohort
Percentage of volunteers who meet the markedly abnormal criteria for safety electrocardiogram (ECG) parameters at least once post dose.	To assess safety NIPRIMUNE in Human	7 days post last dose for each cohort

# **Secondary Outcome Measures**

Outcome Measure	Measure Description	Time Frame
Plasma Cmax	Maximum plasma concentrations	post-dose in Single ascending Dose trial & post dose on days 1 & 7 in Multiple ascending dose part of the trial
Plasma Tmax	Time to Maximum plasma concentrations (tmax)	post-dose in Single ascending Dose trial & post dose on days 1 & 7 in Multiple ascending dose part of the trial
Plasma AUC0-t	Area under the concentration-time curve	Single ascending Dose

Outcome Measure Description		Time Frame	
	from dosing (time 0) to time t [AUC0-t]		
Plasma AUC0-inf	Area under the concentration-time curve from dosing (time 0) extrapolated to infinite time [AUC 0-inf]	Single ascending Dose	
Plasma AUC0-tau	Area under the concentration-time curve to the end of the dosing period [AUC 0-tau]	post dose on days 1 & 7 in Multiple ascending dose part of the trial	
Plasma AUC0-t	Area under the concentration-time curve from dosing (time 0) to time t [AUC0-t]	post dose on day 7 in Multiple ascending dose part of the trial	
Plasma Kel	Elimination constant [Kel]	in Single ascending Dose trial & post-dose on day 7 in Multiple ascending dose part of the trial	
Plasma t1/2	Elimination half life [t1/2]	in Single ascending Dose trial & post dose on day 7 in Multiple ascending dose part of the trial	
Plasma Ctrough	Pre-dose plasma trough concentration (Ctrough)	on days 2 & 6 in Multiple ascending dose part of the trial	

Outcome Measure	Measure Description	Time Frame
Plasma Racc	Accumulation ratio Racc (Cmax on Day 7/Cmax on Day 1), (AUC0-τ on Day 7/AUC0-τ on Day 1) and (Ctrough on Day 1)	post dose on days 1 & 7 in Multiple ascending dose part of the trial

#### **DATA ANALYSIS**

Statistical Analysis: All data will be collected and analysed using the REDCap (Research Electronic Data capture) Descriptive statistics to summarize demographic and baseline characteristics. The analysis will include a description of the study population. Safety analysis: frequency and severity of adverse events. The sample size is estimated to produce a good clinical effect at a 95% confidence and a power of 90 The participants will be randomized into two groups labeled A and B Inferential statistics (e.g., ANOVA, regression analysis) to evaluate dose-proportionality and pharmacokinetic parameters.

#### **Data Collection Forms**

- 1. Consent form
- 2. Schedule of Visits
- 3. Personal Data
- 4. Prior History
- 5. Physical Examination/Vital Signs and Symptoms Monitoring
- 6. Cardiac Study (ECG, Chest X-Ray)
- 7. Haematological Monitoring
- 8. Chemistry Monitoring
- 9. Microbiology Monitoring
- 10. Adverse Experiences/ Concomitant Treatment
- 11. Discontinuation/Termination

## **Anticipated Problems in NIPRIMUNE's Phase 1 clinical trial:**

- a. Patient Recruitment Challenges: Difficulty enrolling participants due to lack of awareness, skepticism about the treatment's efficacy, or concerns about potential risks.
  - i. This problem will be solved by using digital technologies and decentralized trials (other centers to reach a wider audience.
- b. Funding and Resource Constraints due release of funding and resources to conduct the trial effectively.
  - i. Timely release of fund and strict adherence to budget.
- c. Data Quality and Accuracy: Ensuring accurate and reliable data collection and analysis.
  - i. Advanced analytics and real-time data monitoring will be employed to detect any errors to ensure data quality.

# **Budget of Expenditure**

Presented is a detailed budget in relation to the activities and cost.

Activity	Items Required	Cost ( <del>N</del> aira)
Documentation (Secretariat)		
	Laptop (1) and Printer Storage devices, Internet connectivity	N2.500, 000.00
	Stationaries	N500, 000.00
	Statistical package (SPPS)	N300, 000.00
Packing of bulk raw materials, intermediates and processed materials	Storage containers for storage of raw materials and processed materials	N3,500,000.00
	Packaging and labelling materials	N 1, 800,000.00
Extraction of Tank. (Stainless steel, Stirrer, heater and filters)	Fabrication: 2 Stainless Steel tanks with heating and string facility.	12,000, 000.00
Quality Control evaluation of starting materials, NIPRIMUNE	Analytical balances, Glass wares, gloves, phase masks.	4, 850 000.00
	Chemicals and reagents for QC analytical procedures (HPLC grade reagents)	4,100 000.00
	HPLC + extra Column	24,500,000.00
Capsule filling Machine accessories	Size 1	1, 500 000. 00
	Size 2	1, 500 000. 00

Spray dryer	Extract concentration	21, 500, 000. 00
Alternative power supply for 24h/7days power supply.	Diesel purchase, Generator servicing	7,000,000.00
	Sub-total	N85,550,000.00

# **Budget for Clinical Trial**

Activity Category	Subheads	Amount (N)
Pre-study Activities	Protocol development/ Review	1,800,000
	Stakeholders Meetings	1,860,000
	Ethical Approvals	2,250,000
	Protocol Training / Facilitators Meeting	2,250,000
Trial Study	Participants Screening and Enrolment	9,000,000
	(sample collection, lab tests and	
	examination)	
	Follow-up (sample collection, lab tests	4.5,000,000
	and examination)	
	Participant logistic cost (refund of	2,250,000
	transport and lost man-hour)	
Data Management	Digital entry devices	3,000,000
	Software and storage	3,000,000
Study Personnel Cost	Principal Investigators, Co-	30,000,000
	Investigators, Site-PIs, Lab scientists,	
	Nurses, Pharmacists, Social workers, and	
	consultant, Administrative Assistants,	
	Clinical Research Assistant, Data Entry	
	personnel	
Monitors/ Regulatory	NAFDAC and DSMB	1,720,000
compliance		
Logistics: Samples and		3,000,000
personnel movement, and		
communication.		
Clinical Record Materials	CRF, Folders, Lab test request forms,	4.5,000,000
and Stationeries	hand cards, etc	
Report Writing	Report writing, review meetings	4.5,000,000
	Dissemination	2.500,000
Contingencies	10%	9,210,000
Administrative cost	25% of total cost 23,025,000	
	Sub-total Cost	108,330,000
Grand	Total	196,880,000.00

